6.3.2.15. Concentration of velusetrag and THRX-830449 metabolite

Definition

Serial blood samples for assessment of  will be collected 

For each sample, the possible results will be a number indicating the concentration in pg/mL or one of the following other cases: NQ = < Assay LLQ, IS = Insufficient Sample, NR = Not Reportable, or NA =Not Analysed. If results is equal to IS = Insufficient Sample, NR = Not Reportable, NA =Not Analysed or NQ =< Assay LLQ the concentration is not available and will be missing for the summary table and graph.

Analysis methodology

[figure not shown]
Data handling rules

No missing imputation will be performed.

[figure not shown]
| | |
|---|--|
|  | Statistical Analysis Plan |
| | Sponsor: Alfasigma S.p.A. Protocol: VE-CIP2001/2021 |

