11.2.2 Visit 2 (Randomization Visit- V2)

The following procedures will be performed at the randomization visit:

Pre-Randomization:

- 1. 2.
- 3. 4.
- 5. Review and record any AEs that occurred since the previous visit.
- 6. Review and record any concomitant medications taken since the previous visit (attention will be paid to prohibited treatments).
- 7. Re-instruct the subject on how to complete the electronic diary (e-diary), which encompasses the
- 8. e-diary review for eligibility according to inclusion **criterium n 4**. Questionnaires will be completed at the clinical center before randomization if not already completed by the subject.
- 9. Confirmation of inclusion and exclusion criteria.
- 10. completion by the subject.
- 11. Randomization (if still eligible).
- 12. Blood collection (in fasting condition) sample (30 mins prior to drug administration) for proof for absorption.
- 13. Treatment dispensing (if subject has been randomized).

Dosing:

First investigational product dose will be administered under the supervision of the study personnel in the morning, on an empty stomach, with water. Time of dosing will be registered.

After the investigational product administration, the following procedures will be completed:

Post-dose:

- 14. 15. 16.
- 17. Retrain the subject on how to use the electronic diary (e-diary), instructing to complete:
 - The subject will be instructed to record, starting from Day 1, investigational
- product intake information daily.

 18. Schodulo port visit and remind the subject to not to take the investigational product in the
- 18. Schedule next visit and remind the subject to not to take the investigational product in the morning of the next visit, but to take the bottle to the clinic.

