11.2.3 Visit 3 (V3; Day 28±1)

The following procedures will be performed at V3:

- 2. 3.
- 4.
- 5. 6.
- 7. Blood collection (in fasting condition):

- 11. Review and record any concomitant medications taken since the previous visit (attention will be paid to prohibited treatments).
- 12. 13.
- 14.
- 15. Review and record any AEs that occurred since the previous visit.
- 16. Review the e-diary to assess the completeness and retrain the subject as needed.
- 17.

Dosing:

Investigational product dose will be administered under the supervision of the study personnel in the morning, on an empty stomach, with water. Time of dosing will be registered.

After the investigational product administration, the following procedures will be completed:

Post-dose:

- 18. 19.
- 20. Blood samples for analysis for proof of absorption:
- 21. Collect all investigational product bottles and account investigational product.
- 22. Schedule next visit.

11.2.4 Start of Treatment (SOT) Visits: Visit 4 (V4, Day 43 ± 1), Visit 6 (V6, Day 85 ± 1) and Visit 8 (V8, Day 127 ± 1)

The following procedures/assessments will be completed at V4, V6 and V8:

Pre-dose

1.

5.

2. 3. 4.

6. Blood collection (in fasting condition):

- 13. Review and record any AEs that occurred since the previous visit.
- 14. Review the e-diary to assess the completeness and retrain the subject as needed. Questionnaires not yet completed should be completed by the subject at the clinical center before investigational product administration
- 15.
- 16. Dispense investigational product.

Dosing:

Investigational product dose will be administered under the supervision of the study personnel, in the morning, on an empty stomach, with water. Time of dosing will be registered. After the investigational product administration, the following procedures will be completed:

[figure not shown]
Post-dose:

- 17.
- 18. Schedule next visit and remind the subject not to take the investigational product in the morning of the next visit, but to bring the bottle to the clinic, if the visit is scheduled at the clinical center; If the subject cannot go back to the clinical center for the next visit (EOT period), a home visit will be scheduled for the subject.
- 11.2.5 End of Treatment (EOT) Visits: Visit 5 (V5, Day 70 ± 1), Visit 7 (V7, Day 112 ± 1) and Visit 9 (V9, Day 154 ± 1)

The following procedures/assessments will be completed at V5, V7 and V9, if the subject can attend the visit at the clinical center:

Pre-dose

- 1. 2.

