14 PHARMACOKINETIC ENDPOINTS

Not Applicable

[figure not shown]

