3.3.2. Method of Assigning Subjects to Treatment Group

Eligible subjects will be randomly allocated in a 1:1:1:1 manner (4 subjects per treatment sequence), in a blinded fashion, to one of the following four treatment sequences:

- VEL-PLA-VEL-PLA
- PLA-VEL-PLA-VEL
- VEL-PLA-PLA-VEL
- PLA-VEL-VEL-PLA

Where:

VEL= velusetrag 15 mg ([REDACTED] mg [REDACTED]) once a day for 4 weeks.

PLA= matching placebo ([REDACTED]) once a day for 4 weeks.

[figure not shown]
Since the study is a cross-over study, each subject will take both investigational products during the study according to treatment sequence assigned by randomization.

Randomization will be stratified into 3 strata by CIPO diagnosis (idiopathic or secondary to neurodegenerative or demyelinating disease) and by [REDACTED] responder status (responder/naive or non-responder) as follows:

- [REDACTED] non-responder
- [REDACTED] responder/naïve and idiopathic CIPO

[figure not shown]
| | |
|---|--|
|  | Statistical Analysis Plan |
| | Sponsor: Alfasigma S.p.A. Protocol: VE-CIP2001/2021 |

-    responder/naïve and CIPO secondary to neurodegenerative or demyelinating disease.

Non responders are defined as all subjects that, based on investigator's judgement, have an history of a lack of benefit 

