4. DEFINITIONS AND GENERAL METHODOLOGY

4.1. General Methodology

Statistical tables, figures, listings and analyses will be produced using SAS® for Windows release 9.4 or later (SAS Institute Inc., Cary, NC, USA).

Data from all sites will be pooled and summarized. Continuous data will be summarized by the number of observations, mean, standard deviation (SD), median, first and third quartiles (i.e., 25th and 75th percentiles), minimum and maximum. Categorical data will be presented by absolute and relative frequencies (n and %).

All efficacy analyses have the objective to show the superiority of velusetrag over placebo. All statistical analysis will be two-sided at a nominal level of 5%. Confidence intervals will be set at the 95% level.

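### SAP 6.3.2.15 codes assayed results below the LLQ (NQ) as missing, like unusable samples, so mean and median concentrations are biased upward wherever NQ and quantifiable velusetrag samples occur together

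*SAP*

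**What the plan says.** SAP 6.3.2.15 covers plasma velusetrag and its metabolite THRX-830449. On the possible outcomes it says: "For each sample, the possible results will be a number indicating the concentration in pg/mL or one of the following other cases". The other cases are NQ (below the assay LLQ), IS (insufficient sample), NR (not reportable) and NA (not analysed). All four are then handled alike: "NA =Not Analysed or NQ =< Assay LLQ the concentration is not available and will be missing for the summary table and graph". The data handling rule for the section adds: "No missing imputation will be performed".

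The visible text of 6.3.2.15 names no summary statistics. The general rule in SAP 4.1 applies: "Continuous data will be summarized by the number of observations, mean, standard deviation (SD), median, first and third quartiles", plus minimum and maximum. Protocol 16.3 also lists a number of missing observations, not split by cause.

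The samples are taken at V2 and V3, both in treatment period 1. Protocol 11.2.2 shows a pre-dose sample at V2 and says of dosing: "First investigational product dose will be administered under the supervision of the study personnel". Protocol 11.2.3 also has a supervised dose and lists after it: "Blood samples for analysis for proof of absorption". Protocol section 14, "PHARMACOKINETIC ENDPOINTS", is marked not applicable.

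**The concern.** The four codes are not equivalent. IS, NR and NA say nothing about the concentration. NQ says that the sample was assayed and the concentration lies below a known limit. Setting NQ to missing removes values because they are low, so what remains describes only the subjects with measurable drug.

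The samples serve as proof of absorption, so the share of quantifiable samples after a velusetrag dose is the most direct result. Because the doses at V2 and V3 are given under supervision at the site, an NQ shortly after velusetrag says something about absorption or sampling time. Under the rule it drops out of the table and graph in the same way as a lost tube. The summary is then least informative in exactly the situation it should reveal, namely poor absorption in some subjects.

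**Working it through.** The plan gives no LLQ, expected concentration, CV or NQ rate, so there is no figure of its own to reproduce on this point.

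**Direction.** Every NQ value lies below the LLQ and every quantified value lies at or above it. If both occur at a time point, removing the NQ values raises the mean, and raises the median unless ties hold it in place. No distribution needs to be assumed. At the V2 pre-dose sample, and in subjects on placebo in period 1, NQ is the expected result. There the cell is empty rather than biased.

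**Number of subjects.** SAP 3.3.2: "Eligible subjects will be randomly allocated in a 1:1:1:1 manner (4 subjects per treatment sequence"). Two of the four sequences start with velusetrag, so 2 × 4 = 8 subjects contribute velusetrag samples if enrolment goes to plan.

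**Size, scenario 1: one log-normal distribution (assumed), true mean 1.** Let σ² = ln(1 + CV²), q the NQ fraction, z = Φ⁻¹(q) and z′ = Φ⁻¹((1 + q)/2).

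- Mean with NQ dropped, relative to the true mean: Φ(σ − z)/(1 − q)
- Median with NQ dropped, relative to the true median: exp(σz′)
- LLQ that produces q, relative to the true mean: exp(σz − σ²/2)
- Mean with NQ set to LLQ/2: Φ(σ − z) + q × 0.5 × LLQ

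Example, CV 100% and q = 1/8: σ = 0.833, z = −1.150. Mean ratio = 0.976/0.875 = 1.116; LLQ = exp(−0.958 − 0.347) = 0.27.

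| NQ | CV | Mean, NQ dropped | Median, NQ dropped | LLQ needed (share of true mean) | Mean, LLQ/2 |
|---|---|---|---|---|---|
| 1 of 8 | 30% | 1.058 | 1.047 | 68% | 0.968 |
| 1 of 8 | 60% | 1.092 | 1.091 | 45% | 0.984 |
| 1 of 8 | 100% | 1.116 | 1.140 | 27% | 0.993 |
| 2 of 8 | 30% | 1.111 | 1.098 | 79% | 0.932 |
| 2 of 8 | 60% | 1.187 | 1.193 | 59% | 0.964 |
| 2 of 8 | 100% | 1.246 | 1.304 | 40% | 0.985 |

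A simulation of exactly 8 subjects (400,000 draws, lowest one or two values dropped) gives mean ratios of about 1.05-1.11 and 1.10-1.23.

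**The same model read from the LLQ.** If the LLQ is 10% of the true mean, then at CV 100% z = (ln 0.1 + 0.347)/0.833 = −2.349, q = 0.94%, and the mean ratio is 0.9993/0.9906 = 1.009. At CV 60% the bias is about 0.005%. At an LLQ of 5% of the mean it is 0.07% or less.

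**Size, scenario 2: NQ subjects have essentially no drug.** With k such subjects of 8, the true mean is (8 − k)/8 times the mean of the rest, so dropping them overstates it by 8/(8 − k): 8/7 = 1.14 for one, 8/6 = 1.33 for two.

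**The case against.** The strongest objection is to the size. Bias of 6-25% within one log-normal requires an assay limit at 27-79% of the true mean concentration, that is, an assay that barely reaches the level it is meant to measure. Nothing in the documents suggests this, and with an LLQ at a tenth of the mean or lower the distortion is negligible. This stands. A reader might take 6-25% as the expected bias; the documents support it only as a conditional range. The low-LLQ case does not remove the point, because non-absorption, the case that proof of absorption is meant to detect, is outside that model and gives 14% or 33%.

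The analysis methodology of 6.3.2.15 is not shown. It may contain a separate NQ count or other statistics, and Protocol 16.3 counts missing observations. So a reader who infers that the plan hides NQ results goes too far: the codes stay distinct in the data, the rule covers only the summary table and graph, and a count may already be planned. What remains is that the visible rule takes NQ out of the statistics, which a count would not undo. The missing-observations count would pool NQ with unusable samples.

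It is also fair that how many post-dose velusetrag time points are affected cannot be determined from the visible text.

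**Conclusion.** The point holds as a minor one. The upward direction is certain at any time point with both NQ and quantifiable velusetrag samples (ties aside for the median), given that the SAP 4.1 statistics apply. The size is unknown and may be nil. On the assumptions shown it runs from under 1% of the mean (LLQ at 10% of the mean), through about 6-25% (1 or 2 NQ of 8, which needs a high LLQ), to 14% or 33% (one or two subjects with essentially no drug).

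One might infer that the trial's conclusions are at risk. The documents do not support that: no pharmacokinetic endpoint is defined, no visible analysis uses the mean concentration, and the primary and safety analyses do not depend on it.

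**What to change.** In SAP 6.3.2.15:

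1. Treat only IS, NR and NA as missing.
2. Report n (%) quantifiable and n NQ among analysed samples, by actual treatment and time point, as the proof-of-absorption result, unless the text not shown already does so.
3. For the post-dose velusetrag median, keep NQ in the ranking as the lowest values. With all 8 results available the median averages ranks 4 and 5, so up to 3 NQ values leave it the same whatever value below the LLQ they are given. With fewer results, fewer NQ values are tolerated.
4. Prespecify one NQ convention for the mean and graph, and name it as the exception to the no-imputation sentence. LLQ/2 is one example among several acceptable conventions.

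The cost is a few sentences and one recode, with no new data and no change to trial conduct. The downside is that a substituted value is approximate. Under the log-normal assumptions above, LLQ/2 puts the mean about 1-7% too low, a smaller error than dropping NQ in every row of the table.

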6.3.3. Exploratory efficacy analysis

Not applicable.

| | |
|---|--|
|  | Statistical Analysis Plan |
| | Sponsor: Alfasigma S.p.A. Protocol: VE-CIP2001/2021 |

6.4. Safety Evaluation

The safety analyses will be performed on subjects included in the SS.

6.4.1. Extent of Exposure

Exposure time will be computed in weeks within each period of treatment as follows:

$$(Last\ intake\ date\ in\ the\ study\ period - First\ intake\ date\ in\ the\ study\ period + 1) / 7$$

6.4.2. Concomitant medications

 are defined as therapies ending or ongoing after the start of study treatment (i.e., first intake of treatment in the period 1).  will be presented by ATC Code  and Preferred Term by actual treatment on the SS, presenting the number and percentage of subjects with at least one concomitant medication. 

[figure not shown]

| | |
|---|--|
|  | Statistical Analysis Plan |
| | Sponsor: Alfasigma S.p.A. Protocol: VE-CIP2001/2021 |

[figure not shown]

Similarly, medications for CIPO will be presented by ATC Code  and Preferred Term by actual treatment on the Safety Population, presenting the number and percentage of subjects with at least one medication for CIPO. Subjects will be counted once in each category, outputs will be sorted in the overall group by descending frequencies of ATC  and Preferred Term.

Non-drug therapies or surgical and medical procedures

Similarly, non-drug therapies or surgical and medical procedures will be summarized by SOC and Preferred Term by actual treatment on the Safety Population, 

[figure not shown]

6.4.3. Adverse Events

Treatment-emergent adverse events (TEAEs) will be reported by actual treatment. Adverse events starting on or after the first intake of treatment (i.e., first intake in the period 1) are considered TEAEs. 

| | |
|---|--|
|  | Statistical Analysis Plan |
| | Sponsor: Alfasigma S.p.A. Protocol: VE-CIP2001/2021 |

In addition, TEAEs will be summarized by actual treatment, MedDRA System Organ Class and Preferred Terms considering:

- 
- 

Adverse events will be classified as velusetrag emergent if the last treatment taken before the start of the adverse event was velusetrag, or placebo emergent if the last treatment taken before the start of the adverse event was placebo.

In addition, a summary of TEAEs will be provided by treatment sequence. 

[figure not shown]
- 
- 

[figure not shown]

6.4.4. Laboratory parameters

The safety laboratory tests include . The following variables are measured during the study:

- 

| | |
|---|--|
|  | Statistical Analysis Plan |
| | Sponsor: Alfasigma S.p.A. Protocol: VE-CIP2001/2021 |

- 
- 

Of note,  will be collected with different unit of measurements (i.e., sec or ratio). Since there is no conversion factor applicable to uniform the units, these parameters will be summarized separately according to unit of measurements.

- 
- 
- 

[figure not shown]
| | |
|---|--|
|  | Statistical Analysis Plan |
| | Sponsor: Alfasigma S.p.A. Protocol: VE-CIP2001/2021 |

█ 
█ 

6.4.5. Vital signs/Physical examination

Vital signs  and Biometrics measurements 
 will be descriptively analyzed 

6.4.6. Other safety parameters

 (e.g., without artifacts) will be performed and the average of the three readings will be used to determine 
 will be reviewed at the clinical center and final interpretation of all  will be completed by a central reviewer and sent to the site for Investigators' subject evaluation and filing. This final investigation will be considered for the following analyses:

- 
- 

| | |
|---|--|
|  | Statistical Analysis Plan |
| | Sponsor: Alfasigma S.p.A. Protocol: VE-CIP2001/2021 |

Pregnancy test and COVID-19 rapid swab will be only listed.

6.5. Subgroup Analyses

Not applicable.

6.6. Interim Analysis and Data Monitoring

Not applicable.

7. REFERENCES

Not applicable.

